6.5 Procedures

EPIC electronic health records database will allow for availability of demographic data and office-based follow-up records. ProVation MD software information will provide details regarding endoscopic parameters and intervention performed.

Electronic records gathered for study purposes will only be available to study investigators and will be stored on an encrypted hard drive on a computer. Data will initially be entered with PHI attached so that all information can be obtained. Once all data collection is complete identifiers will be removed and random number assigned to the patients.

Upon initial encounter, the study shall be described to the patient in detail by one of the study investigators and informed consent obtained.

Date Last Modified: 10/2/2017

IRB # 2017-0391

CONFIDENTIAL AND PROPRIETARY

Once the patient has agreed to participate, demographic data will be obtained from the medical record including; age, gender, height [inches (in)], weight [pounds (lb)], body mass index (BMI) (lb/in²), past medical history [in particular diagnosis of liver disease, biliary or pancreatic disease, ascites, encephalopathy, portal hypertension, portal hypertension-related bleeding (i.e. varices), liver cancer or masses]. Past surgical history shall be obtained regarding prior cholecystectomy, hepatobiliary or pancreatic surgery (i.e. pancreatojejunostomy) or bariatric surgery (i.e. Roux-en-Y gastric bypass). Medication and social history shall be performed regarding alcohol intake per week and hepatotoxic medications (i.e. acetaminophen). A baseline INR and platelet count shall be performed on all individuals prior to EUS-LB, as is the standard of care.

EUS-LB Protocol

Patients undergoing EUS-LB receive anesthesia during the procedure, as per normal practice. This is provided by a certified registered nurse anesthetist (CRNA). The endosonographic study will be conducted with a linear array echoendoscope (GF-UC140-AL5; Olympus America, Center Valley, PA). Before needle puncture of the desired lobe, color Doppler imaging will be used to ensure the lack of vascular structures in the trajectory of the needle. The EUS-LB will be performed in widely separated regions of the liver using a 19-g EUS-FNA needle (Expect Flexible 19g, Boston Scientific, Marlborough, MA) or a 19-g FNB needle (Acquire 19g, Boston Scientific, Marlborough, MA). A computer-generated randomized schema shall determine needle type selection.

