The left lobe is described as liver parenchyma identified a few centimeters below the gastroesophageal junction with the echoendoscope torqued clockwise. The right lobe is considered the large area of liver tissue can be seen through the duodenal bulb, near the gallbladder [37]. The stylet is removed, heparin flushed through the needle lumen, and the suction device set and attached to the needle hub. The prepared needle is then inserted into the echoendoscope. A transgastric approach will be used to obtain samples from the left lobe of the liver; a transduodenal approach, with the linear echoendoscope positioned in the duodenal bulb, will be used to obtain samples from the large amount of liver parenchyma seen in that location. Once adequate liver parenchymal penetration will be achieved with the needle (~2-6 cm), full suction will be applied with a 20-mL vacuum syringe. One pass consists of a total of 7 to 10 to-and-fro needle motions with the fanning technique applied under direct and continuous endosonographic visualization of the tip of the needle.

The needle will then be removed from the echoendoscope. The specimen will be pushed from the needle with the stylet directly into a microseive, and blood washed from the specimen with a gentle saline rinse. The endosonographer looks for multiple pieces of light brown tissue approximately 5 to 15 mm in length. The tissue cores are then “floated” off the microseive into formalin solution. Heparin is flushed through the needle lumen prior to the next pass. The biopsy process is then repeated on the opposite liver lobe. A pass per liver lobe will be performed in each patient; using the standard 19-g EUS-FNA needle or the 19-g EUS FNB

Date Last Modified: 10/2/2017

IRB # 2017-0391

CONFIDENTIAL AND PROPRIETARY

needle. All patients are closely observed in the recovery area for 1 hour after the procedure, as per our standard policy. Patients will be followed-up with by a phone call the next day and at 1 week after the procedure, as per standard of care.

Sample Processing

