6.8.1 Statistical Analysis Plan

Assuming the 19-g FNB needle has a success percentage of 98% (ie, ≥ 5 portal triads), and margin over FNA needle of 5% (98% vs. 93%), the study needs to evaluate 32 patients to achieve 80% power for a 1-sided non-inferiority test. This also assumes each patient provides 2 specimens. If the margin is increased to 10% (98% vs. 88%), then the study needs to evaluate 18 patients to achieve 80% power.

Descriptive statistics will be utilized to represent continuous and categorical variables, with results expressed as medians with ranges. Multiple comparisons between the aggregate tissue length and CPT yield from bilobar, left lobe only, and right lobe only biopsies will be carried out using the Mann-Whitney-Wilcoxon test. A P-value of <0.05 will be considered statistically significant.

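### The 80% power claimed for 32 patients rests on two specimens per patient with no allowance for their correlation; if the needle is randomised per patient, the design does not have that power.

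*Combined protocol and SAP*

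**What the plan says.** Section 6.8.1 gives the sample size: "Assuming the 19-g FNB needle has a success percentage of 98"%, with a "margin over FNA needle of 5% (98% vs. 93"%), so that "the study needs to evaluate 32 patients to achieve 80% power for a 1-sided non-inferiority test". Success means at least 5 portal triads. The next sentence is "This also assumes each patient provides 2 specimens". A second scenario follows: "If the margin is increased to 10% (98% vs. 88%), then the study needs to evaluate 18 patients to achieve 80% power".

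The section gives no within-patient correlation, design effect, allocation ratio, calculation method or alpha for the non-inferiority test. The only significance level is the general one: "A P-value of <0.05 will be considered statistically significant". No test is named for the success proportion. The one named test, Mann-Whitney-Wilcoxon, is for tissue length and complete portal tracts by bilobar, left-lobe and right-lobe sampling.

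On allocation, section 6.5 says "A computer-generated randomized schema shall determine needle type selection" without giving the unit. Its EUS-LB Protocol part says "A pass per liver lobe will be performed in each patient", with the FNA or the FNB needle, and has the needle flushed before the pass in the other lobe. Section 6.5.1 lists needle randomisation once, on the procedure day.

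**The concern.** The remark about two specimens matters to the sample size only if the second specimen adds information beyond the patient count. Both specimens come from the same liver in the same session and, if the needle is assigned per patient, from the same needle. A positive correlation between them is plausible. The information per arm then lies somewhere between 16 patients and 32 independent specimens.

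A non-inferiority conclusion from about 16 patients per arm depends heavily on which count is used. If the unit of analysis is not fixed, it can be chosen after the data are seen. If the stated power is not real, a failure to show non-inferiority would be hard to interpret.

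**Working it through.** **Inputs.** From section 6.8.1: FNB 98%, FNA 93%, margin 5 points, 32 patients, 2 specimens each, one-sided test, 80% power. Assumed: 1:1 allocation (16 patients and 32 specimens per arm), one-sided alpha 0.05, no dropout, one needle per patient, and ICC of 0.1, 0.3 or 0.5. The documents give no ICC.

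**Step 1. Try to reproduce the 32.** For independent specimens with unpooled variance:

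n per arm = (1.645 + 0.842)² × [p₁(1−p₁) + p₂(1−p₂)] / (p₁ − p₂ + margin)²

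- 98% vs 93%, margin 5: 6.18 × (0.0196 + 0.0651) / 0.10² = 52.4, so 53 specimens or 27 patients per arm: 54 patients, not 32.
- 98% vs 88%, margin 10: 6.18 × (0.0196 + 0.1056) / 0.20² = 19.4, so 20 specimens or 10 patients per arm: 20 patients, against a stated 18.
- One-sided 0.025 needs 67 and 25 specimens per arm.
- If 93% and 88% are only the bounds and both needles are truly 98%, 0.05 needs 97 and 25 specimens per arm.

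No independent-specimen variant tried returns both 32 and 18. The only variant close to both is a paired Wald calculation with one specimen per needle in each patient and the least possible discordance: 6.18 × 0.05 / 0.10² = 30.9 (31 patients) and 6.18 × 0.10 / 0.20² = 15.5 (16 patients). The documents state neither that design nor that assumption.

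**Step 2. Power at 32 patients.** With two specimens per patient on one needle, the design effect is 1 + ICC, so

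n_eff = 32 / (1 + ICC) per arm

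Power = Φ[ 0.10 / √(0.0847 / n_eff) − 1.645 ]

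At ICC 0: √(0.0847 / 32) = 0.0514; 0.10 / 0.0514 = 1.944; Φ(0.299) = 62%.

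| ICC (assumed) | n_eff per arm | Power, 98% vs 93% | Power if both are 98% |
|---|---|---|---|
| 0 | 32 | 62% | 41% |
| 0.1 | 29 | 58% | 39% |
| 0.3 | 25 | 52% | 35% |
| 0.5 | 21 | 48% | 32% |

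The last column uses the same formula with numerator 0.05 and variance 0.0392.

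**Step 3. Clustering alone.** Accept the stated 80% as right under independence. Then power = Φ[ (1.645 + 0.842) / √(1 + ICC) − 1.645 ], and the number needed is 32 × (1 + ICC), rounded up to an even total.

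| ICC (assumed) | Power at 32 patients | Patients for 80% |
|---|---|---|
| 0.1 | 77% | 35.2, so 36 |
| 0.3 | 70% | 41.6, so 42 |
| 0.5 | 65% | 48 |

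**Step 4. Conditional: a specimen-level test that ignores clustering.** One-sided error = 1 − Φ(1.645 / √(1 + ICC)), which is 5.8%, 7.5% and 9.0% at the three ICCs. This is a large-sample approximation. A simulation with 16 patients per arm, two specimens each, true rates of 88% vs 93% and a 5-point margin gave 6.0% at ICC 0, 9.2% at 0.3 and 11.6% at 0.5. The direction agrees, but the decimals cannot be relied on. Near 98% success only 32 × 0.02 = 0.64 failures are expected per arm.

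**The case against.** **Independence is never stated.** A reader might infer that the plan declares the two specimens independent. It does not, and step 1 shows that independent-specimen formulas do not return 32. The method behind 32 is unknown. This stands, but it does not rescue the claim: on the per-patient reading, full independence is more favourable than any positive correlation, and it still gives about 62%.

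**The unit of randomisation is not explicit.** The Sample Processing text in section 6.5 mentions specimens from both lobes and from different needles, which could fit one needle per lobe within a patient. Positive correlation would then make an unpaired test conservative: 1 − Φ(1.645 / √(1 − ICC)) gives about 2.5% at ICC 0.3 and 1.0% at 0.5. The wording fits equally well with needles that differ between patients, and the single randomisation entry and the flushing between passes favour that reading. The point therefore depends on a reading, though the more natural one. Under the other reading the plan would still lack a paired analysis.

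**No planned test is shown to have excess false positives.** A reader might infer that the trial's analysis has an inflated type I error. The documents do not support this. No specimen-level test of the success proportion is specified, and the named Mann-Whitney-Wilcoxon comparisons can use one value per patient. Nor are lost power and excess error joint harms: the first belongs to a test that respects clustering, the second to one that ignores it.

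**Clustering is not the main cause of the gap.** Of the distance from 80%, 18 points exist at ICC 0; clustering adds 4, 10 or 14. This stands.

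**Conclusion.** The concern holds in a limited form. Section 6.8.1 relies on two specimens per patient without allowing for their correlation. On the most natural reading of section 6.5, 32 patients do not give 80% power. The figure is about 62% with fully independent specimens and about 58%, 52% and 48% at ICCs of 0.1, 0.3 and 0.5. If the 80% is granted under independence, clustering alone takes it to about 77%, 70% and 65%.

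These figures rest on assumed 1:1 allocation, assumed one-sided alpha 0.05, an ICC range that is not in the documents, 93% read as the true FNA rate, and a normal approximation that is rough near 98%. The type I error point is secondary and conditional: roughly 6% to 9% over the same ICCs, and only if a specimen-level test that ignores clustering were used.

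**What to change.** State in section 6.5 whether the needle is randomised per patient or per lobe. In section 6.8.1, name the analysis of the needle comparison as one of these:

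- patient as the unit, with the two lobes combined into one result (about 16 versus 16);
- specimens as the unit, with a patient-clustered model or cluster-robust variance;
- a paired analysis, if each patient receives both needles.

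Then restate the power for 32 patients, giving the alpha, the calculation method, whether 93% is the expected FNA rate or the non-inferiority bound, and the design effect 1 + ICC over a stated ICC range. If the lobes are combined, the assumed success rates must be restated for the combined result.

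The cost is SAP wording and a standard analysis, with no extra procedures for patients. The stated power will be less favourable.

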4 HYPOTHESIS AND SPECIFIC AIMS

4.1 Hypothesis

We predict that the 19-g FNA needle and 19-g FNB needle will have similar ability to obtain adequate EUS-LB specimens

4.2 Specific Aim 1

To determine the adequacy of EUS-LB using a 19-g FNB needle as compared with 19-g FNA needle.

4.3 Specific Aim 2

To determine if the 19-g FNB needle will demonstrate less blood artifact during the time of EUS-LB as compared with 19-g FNA needle.

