The surgical pathology department, per a specific protocol for clinical practice, will process the EUS-LB samples. Tissue samples are left in formalin for at least 1 hour before processing. The contents of the formalin jar will be poured into a petri dish, and visible cores of liver tissue picked out with small forceps by the surgical pathology technician. These pieces are arranged in a linear fashion on lens paper, then the specimen photographed alongside a ruler to estimate pre-processing tissue lengths. Samples from both lobes and the different needles will be submitted for evaluation separately. The tissue will be processed in standard fashion, and slide blanks made (5- μ m tissue thickness). These blanks are stained with hematoxylin and eosin, trichrome, and reticulin, with other special stains done as needed. The slides are digitized using a whole slide scanner (ScanScope CS; Aperio Technologies, Inc, Vista, CA), and the digitized images used for quantitative analysis (eSlide Manager; Aperio Technologies, Inc). Quantification of sample length (mm) and portal triads is performed by 2 of the investigators, annotating the digital images with the software. Fellowship-trained GI pathologists then perform histologic interpretation for clinical use.

Post-Procedural Follow-up

After undergoing the procedure, patients will receive a 1 week follow-up phone call to monitor for adverse events (i.e. bleeding), as per standard of care.

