6.6 Primary Endpoints

1. Proportion of cases for which a histologic diagnosis could be made based upon the amount of tissue obtained with the needle.
2. Number of portal tracts (PT) in the specimen [34-36]

Date Last Modified: 10/2/2017

IRB # 2017-0391

CONFIDENTIAL AND PROPRIETARY

3. Aggregate specimen length (ASL), length of the longest piece (LLP), and degree of fragmentation

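### The rank-test sentence in 6.8.1 names no needle, so two listed primary endpoints have no stated FNA versus FNB test; read literally, it applies an unpaired test to paired lobes

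*Combined protocol and SAP*

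**What the plan says.** Section 6.6 lists as primary endpoints "Number of portal tracts (PT) in the specimen" and "Aggregate specimen length (ASL), length of the longest piece (LLP), and degree of fragmentation". Sections 6.1 and 6.5 make needle type the randomised factor.

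On sampling, section 6.5 (EUS-LB Protocol) states: "A pass per liver lobe will be performed in each patient; using the standard 19-g EUS-FNA needle or the 19-g EUS FNB". The second lobe is sampled in the same procedure. Under Sample Processing: "Samples from both lobes and the different needles will be submitted for evaluation separately".

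Section 6.8.1 contains two separate statements on testing.

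- A needle comparison on a binary outcome, at least 5 portal triads: "the study needs to evaluate 32 patients to achieve 80% power for a 1-sided non-inferiority test".
- The rank-test sentence: "Multiple comparisons between the aggregate tissue length and CPT yield from bilobar, left lobe only, and right lobe only biopsies will be carried out", with Mann-Whitney-Wilcoxon as the method. It is followed by "A P-value of <0.05 will be considered statistically significant".

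Section 6.8.2 restates the needle purpose and names no test.

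**The concern.** The rank-test sentence is the only one that assigns a test to length or portal tract yield. It names two outcomes and three tissue sets, and no needle. The contrast must therefore be guessed, and the two possible guesses lead to different analyses.

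- **Literal reading:** the tissue sets are compared with each other. The P-values then answer a question about lobes that is not among the aims. Two primary endpoints go untested between the randomised arms, and the test assumes independence that the sampling scheme rules out.
- **Purposive reading:** FNA is compared with FNB within each set. The test suits the design, but there are three answers per outcome and no rule for which one counts.

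In either case the choice would be left to the analyst after the data are in.

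**Working it through.** The plan gives no figure for the rank tests, so there is none to reproduce. Its 32 patients belong to the binary test and serve here only as the number available.

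**Inputs from the documents.** 32 patients (6.2.1, 6.8.1); one pass in each of two lobes per patient (6.5); threshold 0.05 (6.8.1).

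**Assumptions, because the documents are silent.** Two-sided tests; 1:1 allocation, so 16 per arm; lognormal lobe lengths with SD of log length σ = 0.5, 0.8 or 1.0; within-patient correlation ρ of log lengths from 0 to 0.8; portal tract counts Poisson around length, with 4, 8 or 16 per lobe at median length. The main runs used 4,000 simulated trials per setting.

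**1. Left versus right, literal reading.** The variance of log L − log R is 2σ²(1 − ρ), but an unpaired test works as if it were 2σ². Its true two-sided error is therefore roughly 2[1 − Φ(1.96/√(1 − ρ))]. At ρ = 0.5 this is 1.96/0.707 = 2.77, giving about 0.6%. Simulation with 32 patients and equal lobes:

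| ρ | Mann-Whitney error, length | Mann-Whitney error, count |
|---|---|---|
| 0 | 4.5-4.7% | 4.5-5.4% |
| 0.2 | 2.6-3.3% | 2.7-3.9% |
| 0.5 | 0.7-0.9% | 0.8-2.6% |
| 0.8 | 0-0.02% | 0.02-1.2% |

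Power for length at a left/right ratio of 1.4 and σ = 0.8:

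| ρ | Mann-Whitney | Signed-rank |
|---|---|---|
| 0 | 37% | 33% |
| 0.5 | 31-33% | 55-56% |
| 0.8 | 26% | 90% |

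(The ranges at ρ = 0.5 come from two separate runs.)

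**2. Bilobar versus one lobe, literal reading.** Every patient has both passes, so the bilobar value can only be B = L + R. Then B exceeds L in every patient whose right pass yields tissue, even when the lobes are identical. The null hypothesis is false by design. With 32 patients and identical lobes, P<0.05 occurred in 99.6-100% of trials for length and 96-100% for count at σ = 0.5-1.0. At σ = 1.5 the figure for length was 75-99%.

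**3. FNA versus FNB within each set, purposive reading.** With 16 per arm, one needle and one value per patient, and no true difference, the error of the bilobar test was 4.1-5.3%. For three tests at 0.05, the chance of at least one false result lies between 5% (fully overlapping) and 1 − 0.95³ = 14.3% (independent). Simulation gave 7.0-12.0% for length and 7.7-12.2% for count.

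**4. Which set to make the main one.** At a true needle ratio of 1.5, power was:

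| Outcome | Bilobar | One lobe |
|---|---|---|
| Length | 19-83% | 17-58% |
| Count | 18-78% | 15-51% |

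The bilobar total had the higher power throughout. Even so, P≥0.05 on the bilobar total occurred in 17% (100 − 83) to 82% (100 − 18) of trials despite that difference.

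**5. Unit of analysis.** If the two lobe specimens were entered in the needle test as independent observations, error was 4.2%, 8.4%, 11.1% and 12.4% at ρ = 0, 0.3, 0.5 and 0.7 (σ = 0.5, 1,500 trials each). Hence one value per patient.

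**The case against.** The best defence is that a needle comparison within each set was plainly intended. Sections 4.1, 6.1 and 6.8.2 are all about one needle against the other, and Mann-Whitney-Wilcoxon is the right test for two independent arms. This largely stands. The reading fits the trial's purpose, and on it the test is valid per patient. The pairing and total-against-part faults therefore depend on taking a garbled sentence literally. What the defence cannot supply is the missing wording: the sentence does not name the contrast, the main set or the unit of analysis.

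A reader might infer four stronger things that the documents do not support.

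- *That the plan has no needle comparison.* It has one, the non-inferiority test on at least 5 portal triads.
- *That the hypothesis of similarity will be judged only by P<0.05.* Section 4.1 predicts that the needles "will have similar ability to obtain adequate EUS-LB specimens". That is about adequacy, for which the non-inferiority test is planned. The warning against reading a non-significant result as similarity applies to length and count only.
- *That bilobar versus one lobe must come out significant.* The null is false by design, but significance still depends on sample size and spread, as the 75-99% at σ = 1.5 shows.
- *That one patient may receive both needles.* The Sample Processing phrase on different needles can simply mean needles across patients, and the EUS-LB Protocol text reads as one needle per patient. Confirmation is enough.

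**Conclusion.** The point holds as a defect of specification with a faulty literal reading, and the sentence should be corrected before analysis. No FNA versus FNB test is stated for portal tract count or aggregate specimen length, both listed as primary. This rests on the text alone.

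The sizes rest on assumed inputs. Taken literally, left versus right has error of about 1% and loses much of its power at a lobe correlation of 0.5, but loses nothing if lobes are uncorrelated. The bilobar versus single-lobe P-value carries no information at any correlation. Taken as a needle comparison, the fault is smaller: about 7-12% chance of a false difference per outcome, because no set is named as main.

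Section 6.6 is a numbered list with no stated testing order, so nothing here calls for a hierarchy between count and length. The other primary endpoints and the sample size of the non-inferiority test are outside this point.

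**What to change.** Replace the rank-test sentence in 6.8.1 with:

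> Aggregate specimen length and portal tract count will each be compared between FNA and FNB with the Mann-Whitney-Wilcoxon test, one value per patient (the bilobar total, left plus right), reported with the Hodges-Lehmann difference and 95% confidence interval; left-lobe and right-lobe needle comparisons are supporting. A non-significant P-value for length or count will not be taken as evidence of similarity. Any left-versus-right comparison uses the Wilcoxon signed-rank test within patients. The gain of bilobar over a single lobe is described without a P-value.

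The documents do not rank the sets. The bilobar total is proposed because every patient is planned to have both passes and its power is higher throughout the range examined. The non-inferiority test is left as it is.

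The sponsor should also confirm two points:

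- whether CPT in 6.8.1 and portal tracts in 6.6 are the same count, since the abbreviation list separates complete from partial tracts;
- that both passes in a patient use one needle, so that the two parts of 6.5 agree.

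The cost is wording only, because the lobes are already submitted separately. Single-lobe needle results become supporting. The signed-rank test gives up a little power if lobes are uncorrelated (33% against 37% at σ = 0.8 and ratio 1.4). Two unadjusted bilobar tests leave a 5.5-7.8% chance of at least one false difference. Intervals will be wide: on the ratio scale, about a factor of 1.3 to 2.1 each way for length with 16 per arm.

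### Section 6.8.1 tests length and CPT yield over three overlapping lobe sets at a flat P<0.05 without naming the contrast; read as six needle tests, the family-wise error is roughly 10–22%

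*Combined protocol and SAP*

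**What the plan says.** Section 6.8.1 announces "Multiple comparisons between the aggregate tissue length and CPT yield from bilobar, left lobe only, and right lobe only biopsies", which "will be carried out using the Mann-Whitney-Wilcoxon test". The next sentence sets the only decision rule: "A P-value of <0.05 will be considered statistically significant". The documents give no adjustment, no testing order and no single deciding comparison for these tests.

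Section 6.6 lists portal tract count and aggregate specimen length among the primary endpoints, beside histologic diagnosis, longest piece and fragmentation. I take CPT yield and aggregate tissue length in 6.8.1 to be the measures of those two endpoints.

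Section 6.5 has one pass taken from each lobe in every patient, with needle type chosen by a computer-generated randomisation. It states no allocation ratio.

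The sample-size statement in 6.8.1 concerns a different outcome, success defined as at least 5 portal triads: "the study needs to evaluate 32 patients to achieve 80% power for a 1-sided non-inferiority test".

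**The concern.** Two outcomes over three lobe sets make at least six tests, and any one of them may be called significant at 0.05. The lobe sets overlap: every patient contributes both lobes, so the bilobar value is naturally the left value plus the right. The same tissue is tested alone and again within the total.

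The sentence also names no needle. It could mean FNA against FNB within each lobe set, or one lobe set against another. These readings have different null hypotheses and different error properties, and only the first answers Specific Aim 1.

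At stake is how two listed primary endpoints are interpreted. In a trial of about 32 patients, a left-only or right-only P<0.05 could appear while the bilobar comparison shows nothing, and no rule says which prevails.

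**Working it through.** **Inputs from the documents.** Per-test threshold 0.05; two outcomes; three lobe sets; Mann-Whitney-Wilcoxon (all 6.8.1); about 32 patients (6.2.1); one pass per lobe in each patient (6.5).

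**Assumptions.** Two-sided tests; one needle per patient; 16 patients per needle; bilobar = left + right; between-lobe and length–CPT correlations each varied from 0 to 0.9. The documents give none of these.

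**The plan's own figure.** The only figure is the 0.05 threshold. No family-wise rate is stated, so there is none to reproduce. A single simulated test at 16 v 16 rejects about 4.7% of the time, as it should.

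**Independence benchmark.** Family-wise error = 1 − (1 − 0.05)^k. For k = 6: 1 − 0.95^6 = 0.265, or about 26%.

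**Reading A: six FNA-versus-FNB tests.** Simulation with no needle difference, log-normal outcomes and 20,000 trials per setting. The table gives the chance of at least one P<0.05 among the six tests.

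| Lobe correlation | Outcome correlation 0 | 0.5 | 0.7 | 0.9 |
|---|---|---|---|---|
| 0 | 21.3% | 20.4% | 18.5% | 15.9% |
| 0.3 | 19.6% | 18.5% | 17.0% | 14.8% |
| 0.5 | 17.9% | 17.4% | 15.7% | 13.1% |
| 0.7 | 16.8% | 15.1% | 13.8% | 12.2% |
| 0.9 | 13.3% | 12.8% | 11.7% | 10.4% |

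A separate run gave 21.7% with both correlations at 0. The range is therefore about 10–22%, and as a multiple of the threshold 0.104/0.05 = 2.1 to 0.217/0.05 = 4.3. Even with both correlations at 0 the result stays below 26%, because the bilobar total shares data with each lobe.

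**Reading B: lobe set against lobe set.** There are again six tests (three pairs, two outcomes), simulated with 32 patients and 4,000 trials per setting.

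- Bilobar v left and bilobar v right (four tests): rejected in 100% of trials. The total contains the part, so these are not true nulls and their rejections are not false positives.
- Left v right (two tests): chance of at least one rejection 7–9% with uncorrelated lobes, and about 1.5% at lobe correlation 0.5. The second figure falls below 5% because the rank-sum test treats paired lobes as independent groups.

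The 10–22% does not carry over to this reading. Its faults are trivial contrasts, an unpaired test on paired samples, and no needle comparison for these outcomes.

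**The remedy, checked under Reading A.** Holm on two bilobar tests compares the smaller P-value with 0.05/2 = 0.025 and then, if that passes, the larger with 0.05. Simulated family-wise error for the pair is about 3–5%.

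**The case against.** The strongest defence is that the sentence never says these are needle comparisons, so a multiplicity figure built on that reading is an inference. That stands, and the figure is conditional for that reason. The needle reading is still the more natural one: needle type is what is randomised, no aim or endpoint concerns lobe against lobe, and the rank-sum test suits independent arms. But the text does not settle it.

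Second, 0.05 is a per-test threshold and the plan promises no family-wise rate, so no stated guarantee is broken. That is also true. The point is that several tests on primary endpoints share one significance rule with nothing to say which decides.

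Third, the hypothesis in 4.1 is similarity and the powered test is non-inferiority on another outcome, so a chance lobe-specific difference would not be the trial's stated conclusion. This limits the harm but does not remove it: 6.8.2 describes the purpose as equality or superiority.

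Three stronger readings are not supported:

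- A reader might infer a fixed 14–19%, or three to four times 5%. That needs the needle reading and a narrower choice of correlations (lobe 0.2–0.5, outcome 0.5–0.9), and the documents give no correlation.
- A reader might infer that a count of six tests implies the same error under either reading. Reading B shows that it does not.
- A reader might infer that a single-lobe result would be reported in place of the bilobar one. The documents do not say so; they only leave the question open.

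**Conclusion.** The concern holds in conditional form. The contrast is undefined and the deciding result unnamed for two listed primary outcomes, under one unadjusted threshold. That much rests on the text alone.

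The size depends on the reading. As six needle tests, family-wise error is roughly 10–22%, given the assumed correlations, the 16 v 16 split and two-sided testing. Within that reading the qualitative conclusion does not hang on the correlations, since the lowest value on the grid is still about twice 5%. As lobe-against-lobe tests no such figure applies, and the fault is one of design: contrasts that are not true nulls, ignored pairing, and an untested needle question. Both readings call for rewording before the data are analysed.

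**What to change.** In 6.8.1, replace the multiple-comparisons sentence and, for these tests, the blanket threshold, with wording to this effect:

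- The contrast is FNA versus FNB on the per-patient bilobar total, tested by Mann-Whitney-Wilcoxon for aggregate length and for CPT, two-sided, with Holm across these two tests at an overall 0.05.
- Left-only and right-only needle differences are reported as median differences with confidence intervals, without significance claims.
- Any comparison of one lobe with the other is descriptive and uses a paired method.

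The same edit should confirm that each patient is biopsied with one needle in both lobes, since the per-patient total depends on it.

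The cost is a few sentences and no extra data. Lobe-specific results become descriptive, and the smaller bilobar P-value must be below 0.025 before either outcome can be claimed. The change controls error for length and CPT only. It does not cover the other primary endpoints in 6.6 or the non-inferiority test on at least 5 triads, and the revised text should not suggest that it does.
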